REML	residual/restricted maximum likelihood
RNA	ribonucleic acid
SAE	serious adverse event
SANDE	Symptom Assessment in Dry Eye
SAP	statistical analysis plan
SMQ	standardized MedDRA query
SUSAR	suspected unexpected serious adverse reactions
TBUT	tear breakup time
TFOS DEWS II	Tear Film and Ocular Surface Society Dry Eye Workshop II
TID	ter in die (three times daily)
TNF	tumor necrosis factor
UI	International Unit
US	United States
WHO	World Health Organization

Assessment	A procedure used to generate data required by the study
Clinical Outcome Assessment (COA)	A measure that describes or reflects how a subject feels, functions, or survives
Cohort	A specific group of subjects fulfilling certain criteria
Control drug	A study drug used as a comparator to reduce assessment bias, preserve blinding of investigational drug, assess internal study validity, and/or evaluate comparative effects of the investigational drug.
Discontinuation from study	Point/time when the subject permanently stops receiving the study treatment and further protocol required assessments or follow-up, for any reason. No specific request is made to stop the use of their samples or data.
Discontinuation from study treatment	Point/time when the subject permanently stops receiving the study treatment for any reason (prior to the planned completion of study drug administration, if any). Subject agrees to the other protocol required assessments including follow-up. No specific request is made to stop the use of their samples or data.
Dosage	Dose of the study treatment given to the subject in a time unit (e.g. 100 mg once a day, 75 mg twice a day)
Enrollment	Point/time of subject entry into the study at which informed consent must be obtained (i.e. prior to starting any of the procedures described in the protocol). The action of enrolling one or more subjects.
Estimand	As defined in the ICH E9(R1) addendum, estimand is a precise description of the treatment effect reflecting the clinical question posed by the trial objective. It summarizes at a population-level what the outcomes would be in the same subjects under different treatment conditions being compared. Attributes of an estimand include the population, variable (or endpoint) and treatment of interest, as well as the specification of how the remaining intercurrent events are addressed and a population level summary for the variable.

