6.2 Other treatment(s)

6.2.1 Concomitant therapy

All prescription and over-the-counter medications, procedures, and significant non-drug therapies (including physical therapy and blood transfusions) administered after the subject was enrolled into the study must be recorded on the appropriate electronic Case Report Forms (eCRFs). Concomitant topical ocular medications for reduction of intraocular pressure are permitted.

Each concomitant drug must be individually assessed against all exclusion criteria/prohibited medication. If in doubt, the investigator should contact the Novartis medical monitor before randomizing a subject or allowing a new medication to be started. If the subject is already enrolled, contact Novartis to determine if the subject should continue participation in the study.

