6.2.2 Prohibited medication

Use of the treatments displayed in the below table are not allowed after Screening (Visit 1).

Medication	Prohibition period	Action taken
Ocular, nasal, inhaled, or systemic corticosteroids	During the course of the study	Do not discontinue study treatment but document use of the product in the eCRF
Any topical ocular medications (prescription or over-the-counter; excluding IOP-lowering	During the course of the study	Do not discontinue study treatment but document use of the product in the eCRF
medication)		If the addition of a medication is needed for treatment of an adverse event, the decision to discontinue study treatment will be made by the Investigator and Sponsor based on the relevance and duration of the prohibited treatment
Intravitreal injections of any kind	During the course of the study	Do not discontinue study treatment, but document use of the product in the eCRF
		If the addition of a medication is needed for treatment of an adverse event, the decision to discontinue study treatment will be made by the Investigator and Sponsor based on the relevance and duration of the prohibited treatment
Medical device treatments such as those used to treat Meibomian gland dysfunction (eg, LipiFlow, pulse light therapy, etc)	During the course of the study	Discontinue study treatment
Punctal plugs or punctal cauterization	Placement of new occlusion during the course of the study	Discontinue study treatment

Table 6-2Prohibited medication

Subjects should be discouraged from using artificial tears, gels, lubricants during the study. However, if a subject is in need of occasional rescue and must use these products, the subject can remain in the study but the use of the products must be documented in the eCRF. If a subject is unable to refrain from use of these products and is unable to continue with the requirements of the study, the subject should be discontinued.

Topical ocular prescription medications should be administered at least 10 minutes before dosing with the study medication.

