9.1 Discontinuation

9.1.1 Discontinuation of study treatment

Discontinuation of study treatment for a subject occurs when study treatment is permanently stopped for any reason (prior to the planned completion of study drug administration, if any) and can be initiated by either the subjector the investigator

Discontinuation from study treatment is required under the following circumstances:

- Subject/guardian decision
- Pregnancy
- Use of prohibited treatment as per recommendations in the prohibited treatment section (see Section 6.2.2)
- Any situation in which continued study participation might result in a safety risk to the subject
- Inability or unwillingness of the subject to follow the protocol requirements
- Following emergency unblinding (see Section 6.6.3)
- Adverse events that indicate a safety risk to the subject
- Unsatisfactory therapeutic effect

If discontinuation from study treatment occurs, the investigator should make a reasonable effort to understand the primary reason for the subject's premature discontinuation of study treatment and record this information.

Subjects who discontinue from study treatment agree to return for the end of treatment and follow-up visits indicated in the Assessment Schedule (refer to Section 8).

If the subject cannot or is unwilling to attend any visit(s), the site staff should maintain regular telephone contact with the subject, or with a person pre-designated by the subject. This telephone contact should preferably be done according to the study visit schedule.

After study treatment discontinuation, at a minimum, in abbreviated visits, the following data should be collected at clinic visits or via telephone/email contact:

- New / concomitant treatments
- Adverse Events / Serious Adverse Events

The investigator must also contact the IRT to register the subject's discontinuation from study treatment.

If discontinuation occurs because treatment code has been broken, please refer to Emergency breaking of treatment code section.

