12.4.6 Supplementary analysis

A supplementary clinical question of interest is: what is the effect of ECF843 versus vehicle on change from baseline in signs and symptoms after treatment in subjects with moderate to severe DED, regardless of discontinuation from study treatment for any reason, and regardless of use of artificial tears/gel/lubricants, or prohibited medications?

The supplementary estimands will be the difference between change from baseline in each primary endpoint for ECF843 vs corresponding vehicle, regardless of intercurrent events (treatment policy).

- Use of artificial tears/gels/lubricants: For subjects who use artificial tears/gels/lubricants occasionally for rescue, all observed data will be used for analysis. If not available, missing data on the days of the IEs will be multiple imputed under MAR assumption for both ECF843 and vehicle arms.
- Use of prohibited medications: For subjects who take ocular, nasal, inhaled, or systemic corticosteroids, intravitreal injections of any kind, all observed data will be used for analysis. Missing data on the day(s) + 3 days following the last day of prohibited medications, if any, will be multiple imputed under MAR assumption for both ECF843 arms and vehicle arms.
- For subjects who take the following prohibited medications,
- Any topical ocular medications (prescription or over the counter; excluding IOP-lowering medication)
- Medical device treatments such as those used to treat Meibomian gland dysfunction (eg, LipiFlow, pulse light therapy, etc)
- IVT injections, punctal plugs or punctal cauterization
- all observed data will be used for analysis. If not available, missing data on the days of the IEs will be multiple imputed under MAR assumption for both ECF843 arms and vehicle arms.
- Discontinuation of study treatment
- For subjects who discontinue treatment due to any reason, Retrieved drop-out (RDO) data collected after study treatment discontinuation will be used for analysis. If not available, missing data after treatment discontinuation will be multiple imputed based on J2R assumption for ECF843 arms and under MAR assumption for vehicle arms.
- The supplementary analysis will be performed using MMRM but includes all the observed data and imputed data if appropriate.

Subgroup analyses

Subgroup analyses of the primary endpoints will be outlined in the statistical analysis plan (SAP).

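### Protocol Sections 6.2.1 and 6.2.2 blur stopping treatment and leaving the study, so outcomes the treatment-policy analysis could observe may be imputed instead

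*Protocol*

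**What the plan says.** **Concomitant drugs.** Protocol Section 6.2.1 has each drug checked against the exclusion criteria and the prohibited list, with a call to the sponsor's medical monitor if there is doubt. It then adds: "If the subject is already enrolled, contact Novartis to determine if the subject should continue participation in the study". The glossary defines enrollment as "Point/time of subject entry into the study at which informed consent must be obtained", so the sentence covers randomized subjects but also those who have consented and are not yet randomized.

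**Prohibited medication.** For corticosteroids and topical ocular drugs, Table 6-2 in Section 6.2.2 says "Do not discontinue study treatment but document use of the product in the eCRF", and it says the same in substance for intravitreal injections. For topical and intravitreal drugs given for an adverse event, the investigator and sponsor may decide to stop study treatment. Device treatments and new punctal occlusion call for stopping study treatment.

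**Lubricants.** The paragraph after the table says that with occasional rescue use "the subject can remain in the study but the use of the products must be documented in the eCRF". For a subject who cannot refrain, and who also "is unable to continue with the requirements of the study, the subject should be discontinued", it does not say whether treatment or study is meant.

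**Discontinuation.** Section 9.1.1 lists, as grounds for stopping study treatment, "Use of prohibited treatment as per recommendations in the prohibited treatment section" and "Inability or unwillingness of the subject to follow the protocol requirements". It expects these subjects back for later visits. The minimum data it asks for are concomitant treatments and adverse events. Under Section 9.1.2, leaving the study ends treatment and all further assessments, with a final evaluation if the subject agrees.

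**Analysis.** The supplementary estimand in protocol Section 12.4.6 applies "regardless of use of artificial tears/gel/lubricants, or prohibited medications", and also regardless of treatment discontinuation. SAP Table 2-5 uses all observed data, including data from retrieved drop-outs. Whatever is missing after treatment discontinuation is imputed by jump to reference (J2R) in the ECF843 arms and under missing at random (MAR) in the vehicle arms.

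**The concern.** The protocol defines two different events, stopping treatment and leaving the study. Sections 6.2.1 and 6.2.2 can send a subject to the second for conduct that Table 6-2 and Section 9.1.1 handle as the first, or as no discontinuation at all. That conduct is itself an intercurrent event for which the treatment-policy estimand wants outcomes observed. It is also foreseeable, because inclusion criterion 5 recruits people who regularly use lubricants or feel the need to.

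The supplementary analysis carries some weight here. Protocol Section 12.4.5 and SAP Section 2.5.4.2 plan no sensitivity analysis, so it is the only planned alternative to the MAR handling in the primary analysis. If exits of this kind occurred, part of its result would rest on the imputation model and not on data that could have been collected.

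There is also a consequence for Part 2. Under Section 5, leaving the study in Part 1 bars a subject from Part 2, whereas stopping treatment alone does not automatically do so.

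**Working it through.** **Step 1: follow one subject through the three routes.** Take a randomized subject who uses a doubtful drug, or more lubricant than is occasional.

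| Route | Later SANDE and staining | Primary analysis | Supplementary analysis |
|---|---|---|---|
| Stays on treatment, use documented (Table 6-2) | Collected | Drops event days only, plus 3 days after corticosteroids or intravitreal injections | Uses all observed values |
| Stops treatment, stays in study (9.1.1) | Visits expected, but neither measure is in the minimum dataset | Drops everything after stopping, by design | Uses what was collected, imputes the rest |
| Leaves the study (9.1.2) | None after a final evaluation, if the subject agrees | As the row above | Imputes everything after exit |

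Section 6.2.1 can lead to the third route, and the last lubricant sentence of 6.2.2 can be read that way. Compared with the first route, the primary analysis also loses the subject's later event-free days. Compared with the second, it loses nothing. Moving a subject from the third route to the second does not secure the efficacy data, because the 9.1.1 minimum omits them.

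**Step 2: reproduce the plan's own figure.** Protocol Section 12.8.1 gives n = 112 per arm, a difference of 10 mm, SD 23 mm and two-sided 5% adjusted for 3 comparisons. Taking the adjustment as 0.05/3 = 0.0167:

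- standard error = 23 × √(2/112) = 3.07 mm
- 10/3.07 = 3.25, against a critical value of 2.39
- power = 0.805 (normal) or 0.799 (noncentral t), against the stated 80%

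All 15 cells of Table 12-1 reproduce as well. No stated figure is in dispute.

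**Step 3: illustrate the size.** The documents give no rate of exit for drug or lubricant use, so the share w leaving each arm is assumed. The J2R column supposes that imputation leaves no treatment effect in those subjects and that n stays at 112. The expected difference is then 10 × (1 − w). The other column supposes that leavers contribute nothing at the endpoint, so n = 112 × (1 − w). Power is by noncentral t.

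| w | J2R: difference, power | Reduced n: n, power |
|---|---|---|
| 5% | 9.5 mm, 0.75 | 106, 0.77 |
| 10% | 9.0 mm, 0.70 | 101, 0.75 |
| 20% | 8.0 mm, 0.58 | 90, 0.69 |

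**Step 4: unequal exits.** Let p be the share leaving an arm and b the mean of the imputed minus the true values in those who leave. The between-arm difference shifts by p(ECF843) × b(ECF843) − p(vehicle) × b(vehicle). With 5% against 10% leaving and a common b of 10 mm, the size of the shift is (0.10 − 0.05) × 10 = 0.5 mm. It runs from (0.05 − 0.02) × 5 = 0.15 mm to (0.20 − 0.10) × 20 = 2 mm. A common b is a simplification. J2R and MAR would give different errors, and then equal exit rates could shift the result too.

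**The case against.** The case for leaving the text alone is substantial, and most of it stands.

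- **Section 6.2.1 directs a consultation.** It applies when there is doubt, permits removal without requiring it, and goes through sponsor staff who are masked. A reader might infer that any concomitant drug leads to removal; the text does not say so.
- **Section 6.2.2 sets two conditions and expressly keeps occasional users.** A reader might infer that discontinued means from the study, because the preceding sentence speaks of remaining in it. But Section 9.1.1 lists inability to follow the protocol as a ground for stopping treatment, and Section 9 allows either step. The wording is open, so neither reading can be assumed.
- **Table 6-2 is silent on study participation.** Its conflict with 6.2.1 is by implication.
- **Subjects are not lost from the analysis.** A reader might infer that the treatment-policy analysis drops the very people it is about. The protocol defines FAS 1 by randomization (part of the SAP definition is blacked out), and SAP Table 5-1 keeps prohibited-medication deviations in all analysis sets. Data up to exit remain, Section 8 schedules a final visit, and serious adverse events are reported for 30 days after the last visit. Only values after that are missing.
- **The affected analysis is mainly supplementary.** The primary estimand excludes event-day and post-discontinuation data by design.

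This narrows the point but does not remove it. Study exit is possible under 6.2.1 as written, no criteria govern it, and it ends the collection of outcomes that the supplementary estimand says it will use.

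**Conclusion.** The point holds in a limited form. Sections 6.2.1 and 6.2.2 have to be reconciled with Table 6-2 and Section 9.1.1, because as written they can end follow-up where those provisions address treatment only. The consequence is that obtainable SANDE and staining values after exit would be replaced by J2R or MAR imputations in the supplementary analysis. Some event-free days would also be lost from the primary analysis when the subject would otherwise have stayed on treatment.

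The size is unknown and probably modest. The tables above rest wholly on assumed exit rates and imputation errors, and they do not show an error in the sample size. Nor is a smaller difference under J2R necessarily wrong: if the effect really vanishes once treatment stops, J2R describes that. The difficulty is that the trial would not have observed whether it does. The documents do not support the inference that the primary result is undermined. This is a cheap improvement.

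**What to change.** 1. In 6.2.1 and in the last sentence of the lubricant paragraph of 6.2.2, state whether study treatment or study participation is meant, and make both consistent with Table 6-2 and Section 9.1.1. Which clinical rule applies is for the sponsor to settle.
2. For data collection only, state in both places that use of a concomitant drug or lubricant is not by itself a reason to end data collection in a subject who still consents.
3. In 9.1.1, add the daily SANDE diary and corneal staining to the data sought after treatment discontinuation, next to concomitant treatments and adverse events. Without this, step 1 alone would not protect the supplementary analysis.

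The cost is a few sentences in the protocol and a reminder to sites. A few subjects would stay in follow-up who would otherwise have left. The analysis models and the sample size do not change.

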6.2.2 Prohibited medication

Use of the treatments displayed in the below table are not allowed after Screening (Visit 1).

Medication	Prohibition period	Action taken
Ocular, nasal, inhaled, or systemic corticosteroids	During the course of the study	Do not discontinue study treatment but document use of the product in the eCRF
Any topical ocular medications (prescription or over-the-counter; excluding IOP-lowering	During the course of the study	Do not discontinue study treatment but document use of the product in the eCRF
medication)		If the addition of a medication is needed for treatment of an adverse event, the decision to discontinue study treatment will be made by the Investigator and Sponsor based on the relevance and duration of the prohibited treatment
Intravitreal injections of any kind	During the course of the study	Do not discontinue study treatment, but document use of the product in the eCRF
		If the addition of a medication is needed for treatment of an adverse event, the decision to discontinue study treatment will be made by the Investigator and Sponsor based on the relevance and duration of the prohibited treatment
Medical device treatments such as those used to treat Meibomian gland dysfunction (eg, LipiFlow, pulse light therapy, etc)	During the course of the study	Discontinue study treatment
Punctal plugs or punctal cauterization	Placement of new occlusion during the course of the study	Discontinue study treatment

Table 6-2Prohibited medication

Subjects should be discouraged from using artificial tears, gels, lubricants during the study. However, if a subject is in need of occasional rescue and must use these products, the subject can remain in the study but the use of the products must be documented in the eCRF. If a subject is unable to refrain from use of these products and is unable to continue with the requirements of the study, the subject should be discontinued.

Topical ocular prescription medications should be administered at least 10 minutes before dosing with the study medication.

6.3 Subject numbering, treatment assignment, randomization

6.3.1 Subject numbering

Each subject is identified in the study by a subject Number (subject No.), that is assigned when the subject is enrolled for screening and is retained for the subject throughout his/her participation in the trial. A new subject No. will be assigned at every subsequent enrollment if

Novartis	Confidential	Page 31 of 73
Amended Protocol Version 01 (Clean)		Protocol No. CECF843A2201

the subject is re-screened. The subject No. consists of the Site Number (Site No.) (as assigned by Novartis/Sponsor to the investigative site) with a sequential subject number suffixed to it, so that each subject's participation is numbered uniquely across the entire database. Upon signing the ICF, the subject is assigned to the next sequential subject No. available

6.3.2 Treatment assignment, randomization

Separate randomization lists will be generated for the two parts of the study.

For Part 1, all eligible subjects will be randomized via IRT to one of the treatment arms. The investigator or his/her delegate will contact the IRT after confirming that the subject fulfills all the inclusion/exclusion criteria. The IRT will assign a randomization number to the subject, which will be used to link the subject to a treatment arm and will specify a unique medication number for the first package of study treatment to be dispensed to the subject. The randomization numbers will be generated using the following procedure to ensure that treatment assignment is unbiased and concealed from subjects and investigator staff. A subject randomization list will be produced by the IRT provider using a validated system that automates the random assignment of subject numbers to randomization numbers. These randomization numbers are linked to the different treatment arms, which in turn are linked to medication numbers. A separate medication list will be produced by or under the responsibility of Novartis Global Clinical Supply (GCS) using a validated system that automates the random assignment of packs containing the study treatment.

The same process applies to the subjects eligible to participate in Part 2.

Randomization in both Part 1 and Part 2 will be stratified by subjects with a documented diagnosis of Sjogren's Syndrome. Stratification of subjects with Sjogren's Syndrome is intended to ensure these subjects are evenly distributed across the treatment arms.

The randomization scheme for subjects will be reviewed and approved by a member of the Randomization Office.

